8.3. Screening Visit

All subjects will be screened within 28 days before administration of the study medication to confirm that they meet the subject selection criteria for the study. Subjects who fail screening by not meeting the inclusion and/or exclusion criteria may be rescreened at the Investigator's discretion, within the allowed 4 weeks of screening period.

Subjects will attend the ward, having fasted overnight for at least 10 h.

The following assessments will be done to collect historical safety data, and to assess eligibility for the study:

- Review of inclusion and exclusion criteria
- Complete medical history: including demographic data, previous and concomitant medications (i.e., prescription or non-prescription drugs, and dietary supplements taken within 28 days before the planned dose)
- Full physical examination, including body weight and height: see Section 8.11.3
- Vital signs (BP and HR): see Section 8.11.2;
- 12-lead ECG: see Section 8.11.1
- AE monitoring (spontaneous and solicited AE monitoring will include specific questioning for tolerability and safety)
- Urinary drug screen (opiates, amphetamines, barbiturates, cannabis, benzodiazepines and cocaine-metabolites) and breath test for alcohol
- Blood sampling for serology (HIV and hepatitis)
- Blood sampling for clinical safety laboratory evaluations:
 - Haematology: haemoglobin, haematocrit, MCV, MCH, MCHC, platelets, reticulocytes, WBC including differential, RBC;
 - Coagulation: aPTT, PT;
 - Biochemistry: serum AST, ALT, AP, GGT, LDH, CK, amylase, lipase, glucose, cholesterol (HDL, LDL, total), triglycerides, creatinine, urea, uric acid, bilirubin (total and conjugated), total protein, sodium, potassium, calcium, chloride and magnesium;
 - Urinalysis: by dipstick – glucose, ketone bodies, specific gravity, occult blood, pH, proteins, leucocytes, bilirubin, urobilinogen, nitrites. Microscopy will be done only if the dipstick test for protein, blood, leukocyte esterase or nitrites is abnormal.

To prepare for study participation, subjects will be instructed on the unit- and study-specific restrictions described in Section 4.3 (Dietary and lifestyle guidance).

8.4. Admission to Ward (Day –1)

Subjects will be admitted to the ward at the Phase 1 Unit, on Day –1 at approximately 1600 h, and will have a brief physical exam, urinary drug screen, and alcohol breath test.

Subjects will fast according to the requirements in Section 4.3.

8.5. Profile day (Day 0)

On the morning of Day 0, a cannula will be inserted into a forearm vein, under local anaesthesia with lidocaine 0.5%, for withdrawal of venous blood. Subjects taking Treatment D and E will consume breakfast before their dose (see Section 4.3). Emodepside will be administered, with approximately 240 mL of water²¹, between 0800–1100 h. The following assessments will be done before and/or after dosing at the time points given in the Schedule of assessments (Section 5).

- Scheduled AE monitoring
- 12-lead ECGs
- Vital signs (BP and HR)
- Clinical safety laboratory evaluations (haematology, coagulation, biochemistry, urinalysis)
- Blood sampling to assay emodepside in plasma

8.6. Post-dosing days (Days 1–3)

Subjects will remain on the ward until the morning of Day 3, and have the following assessments at the time points given in the Schedule of assessments (Section 5).

- Scheduled AE monitoring
- 12-lead ECG
- Vital signs (BP and HR)
- Clinical safety laboratory evaluations (haematology, coagulation, biochemistry, urinalysis)
- Blood sampling to assay emodepside in plasma
- Brief (directed) physical examination and short neurological examination

A full neurological examination may be conducted, as required.

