The *in vitro* hERG assay showed no critical potential for QT prolongation (IC₂₀ 19 μ M). *In vitro*, emodepside weakly inhibited GABA-A receptor (46% at 10 mmol/L). In pituitary neuroendocrine preparations, 500 nmol/L emodepside reduced GABAergic activity.

Safety pharmacology and repeated dose toxicity studies revealed the central nervous system as a target organ with changes in behaviour, activity, tremor and gait abnormalities in rats, mice and dogs. A No Observed Adverse Effect Level (NOEL) of 5 mg/kg was defined in dogs and rats after repeated administration (4-week repeat oral dose toxicity study). 10 mg/kg body weight was established as the NOAEL for effects on the nervous system in fasted rats after acute administration. Toxicokinetic (TK) analysis suggested an AUC of 1,611 ng.h/mL and C_{max} of 238 ng/mL after 5 mg/kg/day in dogs following 4-week exposure. In rats, an AUC of 1.9 μ g.h/mL and C_{max} of 79 ng/mL was found following 4 weeks of emodepside given with food at 50 ppm, corresponding to 4.2 mg/kg in males and 5.0 mg/kg in females.

After a single oral application of emodepside to rats, no biologically relevant effect on respiratory parameters was noted (10 – 100 mg/kg). Also in dogs, no effect on respiratory functions was observed at the tested doses. Hyperglycaemia was observed in rats in acute and repeated dose fed studies. Fasted rats were less sensitive with a NOEL of 10 mg/kg body weight compared to fed rats, with a NOEL of 1 mg/kg body weight. Mechanistic studies showed that emodepside inhibited secretory activities in mouse and rat β -cells of the pancreas.

Emodepside showed no adverse effect on electrocardiogram (ECG) results in anesthetized dogs. However, a moderate vasodilatation (reduction of total resistance, slight decrease of arterial blood pressure (BP), moderate, probably reflex tachycardia) was observed at \geq 1.5 mg/kg body weight. A threshold plasma level of 0.1 μ g/mL was determined for this effect. The clinical significance of the vasodilatory effects is unclear as no effect on BP or heart rate (HR) was seen in dogs following oral administration of emodepside for 4 weeks at up to 20 mg/kg body weight.

Summary of pre-clinical pharmacokinetic data

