vision, photophobia (“Increased ocular light sensitivity”), visual impairment (“distorted contrast perception”, “distorted colour perception”) reported by 8 out of 47 subjects receiving emodepside were considered as treatment-related by the Investigator. Also of note, at the highest dose (40 mg), lightheadedness (n=1), dizziness (n=1) or headache (n=1) were reported concomitantly to blurred vision.

None of the volunteers met any of the protocol-specified withdrawal criteria with regards to treatment and overall tolerability to emodepside has been acceptable up to 20 mg. The presence of post-dose visual disturbances in subjects of Cohort 8 receiving either 40 mg solution or placebo may warrant some concern and escalation was stopped at this dose level.

The pharmacokinetic results obtained so far show that T_{max} for the LSF solution is consistently about 1 h post-dose when fasted. Mean C_{max} and AUC for the LSF solution have been roughly dose-proportional, with low to moderate inter-individual variability. The plasma half-life during the first 24 h is very short for a single dose of emodepside. After 3, 7, 16 and 47 h the maximum plasma concentration is reduced to 50%, 25%, 12.5% and 6.25% respectively. Terminal plasma half-life is 523 h. Although data of Cohort 9 (which was treated with a single dose of emodepside with food) are still under review, administration of the LSF of 10 mg with a high fat, high-calorie meal resulted in a clinically relevant food effect with a reduction of AUC to ~67%, C_{max} to 42% and a delay of the T_{max} up to 2.33 h. Therefore, the recommendation of administration of the emodepside (LSF) under fasted conditions is given.

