1.5. Assessment and management of risk

The factors taken into account in the assessment of risk to subjects in this study are as follows:

- The planned single doses of emodepside have been administered to humans and were well tolerated. Based on the FIH single ascending dose clinical study, overall tolerability to emodepside has been acceptable up to 20 mg of LSF formulation. Post-dose visual disturbances were observed more frequently at 40 mg, and although these visual and nervous system disturbances were considered non-serious and mild in intensity, dose escalation was stopped at this dose level. All visual disturbances were transient in nature and resolved spontaneously within 24 h, and without treatment.
- Pre-clinical data suggests that plasma exposure following emodepside as IR-tablets is not higher than the one observed after LSF administration at the same dose.
- In Part 1 of this study, single doses of 5 mg emodepside will be administered in the fed and fasted states. Based on PK data from the FIH study, exposure to emodepside following administration of the IR-tablet in the fed state is likely to be similar to or lower than the IR-tablet administered in the fasted state. Therefore, it is acceptable to test the fed and fasted doses in parallel or sequentially in Part 1.
- Part 2 of this study, in which single doses of 10 mg emodepside will be tested, will proceed only if the PK, safety and tolerability after single doses of 5 mg emodepside in Part 1 are acceptable, and provided the Investigator and Sponsor's Medical Monitor agree that it is appropriate to give a higher dose. The total dose of emodepside for any subject will not exceed 10 mg.

2. Study Objectives and Endpoints

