2.2.2. Secondary Endpoints

- Safety and Tolerability Variables:
 - Adverse Events (AEs)
 - Physical and neurological examination findings
 - Vital signs (BP and HR),
 - 12-lead ECG (HR, PR, QRS, QTcB, QTcF), will be analysed *ad hoc* for safety and for the final data base and report by central reading
 - Clinical laboratory tests
 - Haematology: haemoglobin, haematocrit, mean corpuscular volume (MCV), mean corpuscular haemoglobin (MCH), mean corpuscular haemoglobin concentration (MCHC), platelets, reticulocytes, white blood cells (WBC) including differential, red blood cells (RBC);
 - Coagulation: activated partial thromboplastin time (aPTT), prothrombin time (PT);
 - Biochemistry: serum aspartate aminotransferase (AST), alanine aminotransferase (ALT), alkaline phosphatase (AP), gamma-glutamyl transpeptidase (GGT), lactate dehydrogenase (LDH), creatine kinase (CK), amylase, lipase, glucose, cholesterol (HDL, LDL, total), triglycerides, creatinine, urea, uric acid, bilirubin (total and conjugated), total protein, sodium, potassium, calcium, chloride and magnesium;
- Urinalysis: by dipstick – glucose, ketone bodies, specific gravity, occult blood, pH, proteins, leucocytes, bilirubin, urobilinogen, nitrites and microscopy (reflex).

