Drugs of abuse screen	X	X																								
Alcohol breath test	X	X																								
Physical and neurological examination ²	X	X																		X	X	X	X			
Vital signs ³	X		X			X	X	X	X		X	X					X	X	X	X	X	X	X			
12-lead safety ECG ⁴	X		X			X	X	X	X		X	X					X	X	X	X	X	X	X			
Laboratory safety tests ^{5,6}	X		X																X	X	X	X	X			
Serology ⁷	X																									
Blood samples for assay of emodepside ⁶			X		X	X	X	X	X	X	X	X	X	X	X	X	X	X	X	X	X	X				
AE questioning ⁸			←————→																							

1. Subjects in Part 1a and Part 2 will fast for 10 h before until at least 4 h after dosing. Subjects in Part 1b will be given a high-calorie, high-fat breakfast approximately 30 min before dosing, which they must finish at least 5 min before dosing. Standard meals will be served at approximately 5 h (lunch), 8 h (snack) and 12 h (dinner) after dosing on Day 0. Procedures scheduled at the same time as a meal will be completed before the meal.
2. A full physical examination will be done at Screening and Follow-up. A brief (symptom-directed) physical examination and short neurological examination will be undertaken at all other time points. Any abnormalities will trigger a full neurological examination and/or opening of an AE as appropriate. Height, weight and body mass index (BMI) will be assessed at screening, and weight will be assessed on Day -1.
3. Vital signs will comprise supine blood pressure and heart rate. Subjects should rest in the supine position for at least 10 min before vital signs measurements. Vital signs will be measured in triplicate at screening and pre-dose (-1 h); single measurements at all other time points. Body temperature will be measured on day -1.
4. Subjects should rest in the supine position for 10 min before ECG measurements. Measurement in triplicate at screening and pre-dose (-1 h); single measurements all other time points.

5. Blood and urine samples for clinical laboratory safety tests (haematology, biochemistry, coagulation and urinalysis).
6. Subjects should rest in the supine position for 10 minutes before blood is drawn (if possible).
7. Serology tests will comprise HIV 1 & 2 and hepatitis B & C.
8. Adverse event monitoring will be done throughout the study, but scheduled questioning will be done at the time points of scheduled blood draws.

6. Enrolment procedures

The study will be carried out in healthy male subjects at the following Phase 1 unit:

Hammersmith Medicines Research Limited (HMR),

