8.11.3. Physical examination and neurological examination

Physical examination: will be done by a physician. The following will be examined: general appearance; head, ears, eyes, nose and throat; thyroid; lymph nodes; back and neck; heart; chest; lungs; abdomen; skin; and extremities; and the following systems will be assessed: musculoskeletal and neurological.

At certain time points, as detailed in the Schedule of assessments (Section 5), a brief (symptom-directed) physical and short neurological examination will be performed.

Height and body weight will also be measured at screening; body weight will be measured on Day –1.

Neurological examination will be done by a physician, in case it is clinically indicated, or to investigate treatment-emergent AEs. At the time-points in the Schedule of assessments (Section 5), a short neurological examination will be done, which includes an informal psychological assessment (e.g. orientation to place and time). Any abnormalities will trigger the full neurological examination or opening of an AE as appropriate. The full neurological examination may include (but is not limited to) any of the following: alertness, speech, language, and comprehension; cranial nerves; motor exam; coordination/cerebellar function; tremor of the hands, legs and head (postural, kinetic and rest tremor); sensation; gait and postural stability (Pull test);

mood; and sleepiness. Abnormalities assessed as clinically significant will be reported as adverse event (see AE definition in Section 9.1).

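### No neurological examination is scheduled on the dosing day, so normal scheduled findings say little about effects near peak concentration

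*Protocol*

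**What the plan says.** - **Endpoint.** Protocol 2.2.2 (and SAP 4.2.2) names "Physical and neurological examination findings" among the safety variables, under a secondary objective of comparing the safety and tolerability of the formulations.
- **Reason for interest.** Protocol 1.3: "Safety pharmacology and repeated dose toxicity studies revealed the central nervous system as a target organ". This refers to animal studies.
- **Day 0.** Protocol 8.5 says "The following assessments will be done before and/or after dosing at the time points given in the Schedule of assessments (Section 5") and then lists AE monitoring, ECG, vital signs, safety laboratory tests and PK sampling. No physical or neurological examination is on the list, and neither schedule table has a Day 0 mark in that row.
- **After dosing.** Protocol 8.6 (Days 1–3) is the first post-dose list to include "Brief (directed) physical examination and short neurological examination". Section 8.7 repeats a short neurological examination on Days 5 and 7.
- **Before dosing.** The schedule row is marked at Screening and Day −1. Footnote 2 to the Section 5 schedule says: "A brief (symptom-directed) physical examination and short neurological examination will be undertaken at all other time points". Section 8.4 names only a brief physical examination on Day −1.
- **Unscheduled route.** Protocol 8.11.3: "Neurological examination will be done by a physician, in case it is clinically indicated, or to investigate treatment-emergent AEs".
- **Reporting.** SAP 14.6.3 and Listing 16.2.9.5 list abnormal findings only. No count of men examined is planned.

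**The concern.** The schedule looks at the nervous system before dosing and again from Day 1, and leaves out the hours around peak concentration. If a tablet produced a brief objective sign near peak in a man who noticed nothing, no scheduled examination would be there to record it.

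The listing adds to this. An empty listing of abnormal findings cannot separate no sign near peak from nobody examined near peak, because it has no denominator and no time point in that period. The endpoint serves a comparison between formulations, and safety and tolerability data also go to the Safety Review Group before the 10 mg part (Protocol 7.5).

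**Working it through.** **1. When the examinations fall.** The schedule table does not read reliably by column, so I checked its time axis against Table 4 (Protocol 8.10).
- PK times: pre-dose, then 0.25, 0.5, 1, 1.5, 2, 2.5, 3, 4, 6, 8, 12, 24, 36, 48, 72, 120 and 168 h. That is 1 + 17 = 18, as in Table 4.
- Laboratory times: Screening, pre-dose, 24, 48, 72, 120 and 168 h. That is 7, as in Table 4.
- Volume: 14 + 17.5 + 21 + 2.5 + 90 + 13 = 158 mL, as stated.

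The examination row in the SAP has five post-dose marks, the same number as the laboratory row. This fits Days 1, 2, 3, 5 and 7 in Protocol 8.6 and 8.7, with the first at 24 h. The protocol row appears to have four, and I draw nothing from the difference. In neither is there a mark on Day 0, so the first scheduled post-dose examination is on Day 1 at the earliest.

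**2. Concentration at that time.** Protocol 1.4 gives, for the solution: "After 3, 7, 16 and 47 h the maximum plasma concentration is reduced to 50%, 25%, 12.5% and 6.25% respectively". Between 16 h and 47 h the concentration halves once in 31 h. By log-linear interpolation:
- Times counted from dosing: 12.5% × 2^(−8/31) = 10.5% of Cmax at 24 h.
- Times counted from a peak at 1 h: 12.5% × 2^(−7/31) = 10.7%.
- For comparison, with a peak at 1 h, the level at 2 h is 100% × 2^(−1/3) = 79.4%.
- At 48 h it is about 6%.

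**3. When effects occurred in the first-in-human study (Protocol 1.4, 1.5).**

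| Effect | Onset | Duration |
|---|---|---|
| Visual disturbances | Cohort 10 (40 mg): mostly close to Tmax | All resolved within 24 h (1.5); Cohort 10 durations described only as various |
| Oral paresthesia (one man, 40 mg) | Not stated | About 6 h |
| Headache, dizziness, somnolence | Not stated | Not stated |

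On the visual effects Section 1.5 says: "All visual disturbances were transient in nature and resolved spontaneously within 24 h, and without treatment". The solution's Tmax was about 1 h fasted and up to 2.33 h with food. Tablet Tmax is not given.

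**4. How often.** In Cohorts 1–8, nervous-system TEAEs occurred in 10/47 = 21.3% of exposed men and 2/16 = 12.5% on placebo. Eye TEAEs occurred in 9/47 = 19.1%, and 5 of those 9 men had 40 mg. At the doses used here, Table 1 of Protocol 1.4 has one man with a nervous-system TEAE in each of the 5 mg solution, 5 mg tablet and 10 mg solution groups: 3 of 11 + 6 = 17, or 17.6%. (The printed n and percentages of the two 5 mg groups do not match, but the two groups sum to 11 either way.) No abnormal objective neurological finding was reported. If all 47 were examined, the one-sided 95% upper bound is 1 − 0.05^(1/47) = 6.2%.

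**5. What covers Day 0 now.** Footnote 8 of the schedule ties AE questioning to each blood draw, which gives 11 post-dose questionings on Day 0 (0.25 to 12 h). A reported symptom can trigger an examination under 8.11.3. A man who reports none is not examined that day.

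**6. What a Day 0 examination could show.** If every result were normal, the one-sided 95% upper bound on the rate of abnormal findings would be 1 − 0.05^(1/12) = 22.1% in an arm of 12, and 1 − 0.05^(1/60) = 4.9% over the 60 men of Part 1.

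**The case against.** The other side has real strength.

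- **The known human effects are symptoms.** Blurred vision, photophobia, headache and dizziness are what AE questioning picks up, and every man is asked repeatedly around peak. TEAEs are tabulated by treatment with N, so the tolerability comparison already has a Day 0 measure with a denominator. This stands. It limits the gap to objective signs without symptoms.
- **The first-in-human study found nothing on objective examination**, with doses up to 40 mg against 5 or 10 mg here. This also stands as a reason to expect normal findings whatever the timing. The protocol does not say when those examinations were done, so it does not show that examining near peak is uninformative.
- **The short examination is modest.** The only content Section 8.11.3 describes for it is an informal psychological assessment such as orientation. That limits what it can find. Still, one man in Cohort 10 (40 mg) had balance disorder and disorientation, which an examination could pick up.
- **Twelve men per arm cannot compare arms on rare signs.** True, as step 6 shows. The gain is a recorded observation at a relevant time with a denominator, not a powered comparison.
- **Section 8.8 already lets time points be added or changed with the Sponsor's approval.** That lowers the cost of the change but leaves it to discretion.

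A reader might go further and infer that the drug's known nervous-system effects are over by the first post-dose examination. The documents say this for visual disturbances only; durations of dizziness, headache and somnolence are not stated.

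**Conclusion.** The gap is real and narrow. No neurological examination is scheduled on Day 0. The first post-dose one comes on Day 1 at the earliest, at about 10.5% to 10.7% of Cmax and, for visual disturbances at least, after the effects had resolved in the first-in-human study. Normal scheduled findings therefore say little about objective signs near peak in men who report no symptoms.

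This rests on the solution's decay figures, with log-linear interpolation, carrying over roughly to the tablets.

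Three stronger readings are not supported. The documents do not show that the listing would be empty because of timing, given the first-in-human result. They do not show that symptomatic men go unexamined on Day 0, given 8.11.3. And nothing says the Safety Review Group would rely on this listing alone, since it reviews all safety, tolerability and PK data. The point is a cheap improvement to a secondary endpoint. It does not affect the primary PK comparison.

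**What to change.** In Protocol Section 5, 8.5 and 8.6, and in SAP Section 6:

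1. Move one existing late short neurological examination, for example the Day 2 one, to Day 0 near expected Tmax, after a PK draw. Section 8.2 already puts physical examinations last in the order of procedures. A window of about 1–2 h fasted and 2–3 h fed is an assumption taken from the solution's Tmax, and should be stated as such.
2. Use the Day −1 examination as its baseline. For this, reconcile Section 8.4 (brief physical examination only) with schedule footnote 2 (short neurological examination as well).
3. In SAP 14.6.3, add the number examined and the number abnormal by arm at the Day 0 time point. Keep Listing 16.2.9.5.

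Apply the same timing rule to every arm, so that the counts can be set side by side.

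**Cost.** A schedule change, for which Section 8.8 may already give room. The number of examinations per man stays the same. The downside is one fewer late examination and a few minutes of physician time in a busy window: PK draws are 30 minutes apart from 0.5 to 3 h with a 5-minute tolerance, and 10 minutes of supine rest are required before ECG and vital signs.
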